17.0 Data Management and Confidentiality

17.1 Data analysis plan

Statistical power and sample size for Aim 1:

All 377 children randomized in Omega Tots will be eligible for follow-up. We estimate power based on a conservative estimate of 300 children (80%) attending the age 8 ½ - 10 ½ visit. To evaluate differences between the treatment arms, 300 children divided equally to each arm provides >80% power to detect a 0.32-SD mean difference or larger (Cohen's $d \geq 0.32$) in each of our primary outcome measures: DAS-II GCA (general cognitive ability), CELF-Core Language (language), or Toolbox Executive Function factor (EF) ($\alpha=0.05$) at age 8 ½ - 10 ½ (Hypothesis 1). This effect size is the same or smaller than what the DINO trial observed on the BRIEF at age 7, and the short (ECBQ) and follow-up (DP-3 at age 2) results from Omega Tots. These effect sizes are also similar in magnitude to the (beneficial) effect observed in the Infant Health and Development Program early intervention trial at age 8 on IQ and reading and math achievement among infants born at 2000-2500g. Sub-group analyses will necessarily be exploratory because only a much larger sample would be fully powered to test the interactions of interest. But, these are worth exploring because in the original Omega Tots trial we observed 2 statistically significant sub-group effects. Although it would be ideal to employ a repeated measures analysis using the 3 available time points (trial, age 2, age 8 ½ - 10 ½), robust developmental measures that are comparable at all time points are not available. We will pursue longitudinal analyses for the secondary outcomes where repeated measures exist, however.

Statistical analysis for Aim 1:

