Analyses for Aim 1 will follow intent to treat principles, the most rigorous approach to RCT data. By using intent to treat we are able to detect lasting effects of DHA+AA supplementation if they are present at the magnitude we anticipate. Children who were randomized but discontinued taking treatment or were lost to follow-up will be included in analyses. Our main goal will be to estimate the effect of treatment assignment on our 3 primary outcomes at age 8½ - 10 ½ (DAS-II GCA, CELF-5 language, Toolbox EF) using the following mixed model, consistent with the analysis of our Omega Tots trial: $y_{it} = \beta_0 + \beta_1 Time_t + \beta_2 Time_t \times Trt_i + \epsilon_{it}$, where implicitly it is assumed that there is no main effect of Trt_i , y_{it} is the outcome of interest at time t , $Time_t$ is coded as 0 for the outcome at baseline (i.e., the covariate for our purposes here) and 1 for the post-randomization measure of the outcome obtained at age 8 ½ - 10 ½, and the primary effect of interest is β_2 , which corresponds to the difference between groups on the outcome at age 8 ½ - 10 ½. In this model, the baseline measure of the outcome is constrained to have equal means across groups by assuming there is no main effect of the intervention, Trt_i . This constraint yields a statistical test for β_2 analogous to the test of the treatment group main effect via ANCOVA controlling for the baseline measure without requiring list-wise deletion due to missing data. Specifically, our model is estimated using maximum likelihood estimation, and therefore allows for outcome data at either time point to be missing at random. We will account for clustering due to twins/triplets in our sample by adding a random effect at the family level. Exploratory pre-specified sub-group analyses will proceed by testing interaction terms added to the models for sex, birthweight (<1500g vs ≥ 1500 g), socioeconomic (household income dichotomized at the median), and daily dietary intake of DHA plus EPA (below vs above the median).

PROTOCOL TITLE: Long-term Effects and Safety of DHA+AA Supplementation in Toddlerhood for Children born Preterm

Interactions with $p < .20$ will be considered statistically significant, and stratified results will be reported consequently. Analyses will use the MIXED procedure, SAS 9.4.

Statistical power, sample size, and analysis for Aim 2 (i.e. genetic biospecimens):

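### Birthweight, household income and DHA+EPA intake enter the exploratory interaction tests only as two-level groups, which costs power if the supplement effect varies gradually with them

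*Combined protocol and SAP*

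**What the plan says.** The sub-group tests are described in section 17.1, under the statistical analysis for Aim 1. They proceed by "testing interaction terms added to the models for sex, birthweight" (below 1500 g against 1500 g or more), "socioeconomic (household income dichotomized at the median), and daily dietary intake of DHA plus EPA (below vs above the median"). Sex is binary by nature; the other three are quantities or ordered categories reduced to two groups. Interactions with p below .20 "will be considered statistically significant, and stratified results will be reported consequently".

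The power text in the same section is open about the limits: "Sub-group analyses will necessarily be exploratory because only a much larger sample would be fully powered to test the interactions of interest". It gives no power figure for any interaction.

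No continuous treatment-by-modifier term appears elsewhere for these three variables. The additional analyses at the end of section 17.1 correlate dietary fatty acid intake with outcomes, but that is not a treatment interaction. The documents give no reason for the cuts, no distribution for the three modifiers and no share of children below 1500 g.

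**The concern.** Cutting a quantity in two treats a child just below the cut as different from one just above it, and as the same as the most extreme child in that half. If the supplement effect changes gradually across the modifier, the within-half variation that carries part of the signal is discarded.

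The sample cannot exceed the 377 children randomised, so the coding of the modifier is one of the few ways left to gain power. Section 3.0 reports that the original trial saw adverse effects in two pre-specified sub-groups, and section 2.1 says the study should either reassure about safety or draw attention to lasting harm. A missed modifier could hide an effect confined to some children. Because stratified results follow only when an interaction passes p<.20, a miss also changes what is reported.

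**Working it through.** **Inputs from section 17.1.** "We estimate power based on a conservative estimate of 300 children (80%) attending the age" is the planning basis (300/377 = 79.6%); allocation is equal, so 150 per arm; alpha is 0.05 for the main effect (two-sided assumed, as sidedness is not stated); the interaction threshold is p<.20.

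**Assumptions of this check.** Residual SD 1; linear interaction; slopes b of 0.2 and 0.3 SD change in treatment effect per SD of modifier. The slopes are not from the documents. Twin and triplet clustering and baseline adjustment are ignored; they would change absolute power but have little effect on the ratio between codings.

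**1. The plan's own figure.** The plan states that "300 children divided equally to each arm provides >80% power to detect a 0.32-SD mean difference or larger". With a standard error of √(2/150) = 0.1155, 0.32/0.1155 = 2.771, and power = Φ(2.771 − 1.960) = 79.1% (78.9% by noncentral t). This reproduces the figure to within rounding, just under the stated value before any gain from baseline adjustment.

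**2. Information kept by a cut.** This is the squared correlation between the modifier and its two-group version. For a normal modifier with a fraction p below cut c (on the standard normal scale) it is φ(c)²/[p(1 − p)]; at the median it is 2/π = 0.637. The loss is 36.3%: 300 × 0.637 = 191, so 300 children act like about 191 for that test.

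| Modifier and cut (linear effect) | Information lost |
|---|---|
| Uniform, median | 25% |
| Normal, median | 36% |
| Normal, 40/60, 30/70, 20/80 | 38%, 42%, 51% |
| Gamma (shape 2), median | 45% |
| Exponential, median | 52% |
| Lognormal (log-SD 0.5 to 1.0), median | 48% to 73% |

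The skewed rows assume that the effect is linear in the untransformed modifier.

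**3. Power at p<.20 (normal modifier, median split).** For a continuous term, noncentrality = b√300/2. For the split, multiply by √(2/π) = 0.798. The two-sided critical value is 1.282, and both tails are counted.

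| b | Noncentrality, continuous | Noncentrality, split | Power, continuous | Power, split |
|---|---|---|---|---|
| 0.2 | 1.732 | 1.382 | about 67% | about 54% |
| 0.3 | 2.598 | 2.073 | about 91% | about 79% |

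A slope of 0.2 corresponds to about 0.32 SD between the two halves (0.2 × 2 × 0.798). A simulation of 4,000 trials at b = 0.2 gave 67% and 53%, with an information loss of 39%.

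**4. Detectable effect.** With four cells of 75, the split's standard error is √(4/75) = 0.231. At p<.20 and 80% power it detects a between-half difference of 0.231 × (1.282 + 0.842) = 0.49 SD. The continuous term detects the equivalent of 0.49 × 0.798 = 0.39 SD.

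**5. If linearity fails.** When the effect was simulated as a step of 0.32 SD at the median, the split did better: 51% power against 43% for the linear term at p<.20.

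**The case against.** The case for leaving the plan alone has four parts.

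- *The tests are exploratory and their weakness is disclosed.* This stands, and it limits the stakes. It does not explain why available information is left unused.
- *The p<.20 threshold already compensates.* It raises power under both codings, but a gap of about 12 to 13 points remains. The threshold buys sensitivity by accepting more false positives; a continuous term does not, provided linearity is reasonable.
- *Fixed groups may preserve comparability with the original trial.* This is possible, and it is a good reason to keep reporting them. It does not require that they be the only test.
- *A continuous term has costs of its own.* It assumes linearity and loses to the split if the truth is a step at the cut. A log transform fails for zero intake, and the gain shrinks if income was recorded in a few bands. All of this stands and shapes the fix. The plan does not argue for a step at any of these cuts.

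A reader might also infer that the median groups shift with attrition and will not match the original trial. The documents do not support that. They do not say whose median is used, and since section 17.1 includes children lost to follow-up in the analyses, a median over all 377 is compatible with the text. The original trial's cuts are not given. The 1500 g cut is fixed in any case.

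**Conclusion.** The point holds as a conditional loss of efficiency in exploratory tests. For a normal modifier, a median cut and a linear interaction, the loss is about 36% of the information, or 12 to 13 points of power at the plan's own threshold for the slopes assumed. With a linear effect, other plausible shapes put the information loss between about 25% and over 50%; with a step at the cut there is none.

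Two stronger readings are tempting and should be resisted. One is that a third of the information is lost for all three modifiers. The documents give no distributions, and birthweight has a fixed cut with an unknown split. The other is to quote power at 0.05, where b = 0.2 gives 41% falling to 28%. The plan tests interactions at p<.20, so those absolute figures are too low for this plan. The loss is also one of information: power does not fall by a third. The primary treatment comparison is untouched.

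**What to change.** In section 17.1, pre-specify the interaction test for birthweight, income and DHA+EPA intake with the modifier as a continuous or ordered-category term, together with its lower-order terms.

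- Name the scale in advance: grams for birthweight; for intake, a transform that allows zeros, such as log(x + c) with c stated, or ranks; for income, category scores if it was collected in bands.
- Report the treatment effect with its confidence interval at the 25th and 75th percentiles of each modifier.
- Check linearity once, for example with a restricted cubic spline.
- Keep the pre-specified 1500 g and median-split results as supporting presentation.
- State whose median defines the groups, since the text leaves this open.

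The cost is SAP wording: the same data and the same modelling framework, with no new participants. The downside is a linearity assumption and some loss of power if the true effect is a threshold at the cut; the retained two-group results would still show such a pattern.

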2.1 Hypotheses & Aims

Our central hypothesis is that preterm children who were randomized to 180 days of DHA+AA at age 1 will exhibit poorer general cognitive ability, greater language deficits, and more impaired executive function at age 8½ -10½ vs children randomized to placebo. Our hypothesis has been formulated primarily on the findings from Omega Tots and DINO, the largest DHA-supplementation trial of preterm infants. The rationale for this project is that a careful examination of the long-term effects of DHA+AA supplementation will offer much-needed clarification about the appropriateness of DHA+AA as an intervention to promote neurodevelopment among children born preterm. We plan to pursue our central hypothesis and accomplish our objective by pursuing the following specific aims:

Aim 1: Determine the long-term effect of DHA+AA supplementation at age 1 year by comparing general cognitive ability, language, and multiple facets of executive function between the DHA+AA and placebo arms at age 8-9.

- Based on our preliminary data, working hypothesis 1 is that children randomized to DHA+AA at age 1 will display at least a 0.3-SD (effect size) deficit on measures of general cognitive ability, language, executive function at age 8½ - 10½ vs placebo.
- Sub-aim 1: Explore sub-group differences by sex, birthweight, socioeconomic status, and diet.

PROTOCOL TITLE: Long-term Effects and Safety of DHA+AA Supplementation in Toddlerhood for Children born Preterm

Aim 2: Determine the role of variability in fatty acid metabolism genetics en masse on the effect of DHA+AA supplementation on short and long-term outcomes, and further focus on 2 previously published FADS2 genetic variants.

- Based on prior observational studies, working hypothesis 2a is that common genetic variant-based heritability over long-chain fatty acid metabolism will be associated with poorer performance on our outcome assessments at ages 1, 2, and 8½ - 10½ years for children assigned to DHA+AA vs placebo. Genetic variation is based on measured SNPs in genes accounting for virtually all synthesis of very long-chain fatty acids. Further, we hypothesize (2b) that minor allele status for FADS2 rs1535 and rs174575, the most commonly replicated SNPs in the literature, will be associated with poorer outcomes for children assigned to DHA+AA, vs placebo.

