To address the first part of Aim 2, we apply the standard method for estimating SNP-based heritability, which assumes the common SNP effect is a random effect in a mixed linear model and with variance decomposed into variance components for genetic and non-genetic effects. The generic model is therefore specified as: $y = \beta_0 + X\beta + g + \epsilon$, where g is the random genetic effect and further the model is constrained by $V = A\sigma_g^2 + I\sigma_e^2$ where V is the overall variance decomposed into genetic and non-genetic (i.e. environmental) components; the matrix A is the genetic relationship matrix, which is similar to the concept of a distance matrix in geospatial modeling, though in this case the distance is genetic similarity calculated from the genome-wide SNP data. Therefore, genetic effects are associated with the covariance matrix for common SNPs (called A) and non-genetic effects with the identity matrix (called I). Using the identity matrix for this purpose assumes no shared environment effects, which is valid since only unrelated persons are included in the calculation. We routinely assess age, sex, and socioeconomic status as covariates, and always include ancestry principal components. SNP-based heritability can be performed on case-control datasets, population cohorts or other collections of unrelated individuals. Thus, while traditional heritability assumes zero genetic covariance between “unrelated” persons, observed SNP-based genetic covariance will rarely if ever be zero. The cohort includes mostly unrelated individuals (55 sets of twins/triplets). Rather than model the relationships among related individuals and lose power from increased degrees of freedom, we will apply a resampling procedure. Sampled datasets with 1 twin chosen at random ensures the datasets in each replicate contain only unrelated persons but the average over the sampled datasets converges on estimates that use information from all children. In our cohort we will have $>80\%$ power to detect SNP-based heritabilities as low as 21%, after accounting for the resampling procedure. While fatty acid markers have not explicitly been tested this way before, the relationship between genetics and many metabolism biomarkers in blood is much higher than a heritability of 21%, giving further reassurance that the study is adequately powered. The test of *en masse* SNP effects in the context of this clinical trial takes the form similar to Aim 1, $y_{it} = \beta_0 + \beta_1 Time_{it} + \beta_2 Trt_{it} + \beta_3 g + \beta_4 Trtxg + \beta_5 Timexg + \beta_6 Time_i Trt_i + \beta_7 Time_i x Trtxg_i + \epsilon_{it}$, while the constraints on V are still imposed. The matrix A will be estimated using the software GCTA and the model will be tested using R or Python depending on whether numerical issues arise in the numerical matrix calculations. We can perform this model using structural equation models implemented in the R library genomicSEM. This modeling platform will allow us to use *en masse* SNPs in the models described above.

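### The en masse SNP model for Aim 2 keeps V = Aσg² + Iσe² with two scores per child, so its genetic variance absorbs stable non-genetic differences between children.

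*Combined protocol and SAP*

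**What the plan says.** All of this stands in section 17.1 unless noted.

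- The generic heritability model has one response per person and V = Aσg² + Iσe². A is the SNP-based relationship matrix; everything non-genetic goes with the identity matrix. The reason given is: "Using the identity matrix for this purpose assumes no shared environment effects, which is valid since only unrelated persons are included in the calculation".
- The plan then says that the test of en masse "SNP effects in the context of this clinical trial takes the form similar to Aim 1". It writes the model for y_it with Time, Trt, g and their interactions, "while the constraints on V are still imposed".
- Under Aim 1, Time "is coded as 0 for the outcome at baseline (i.e., the covariate for our purposes here) and 1 for the post-randomization measure of the outcome". Each child therefore contributes two rows. Hypothesis 2a (section 2.1) reaches further: the genetic component "will be associated with poorer performance on our outcome assessments at ages 1, 2, and 8½ - 10½ years".
- Sibling likeness is handled in Aim 2 by repeatedly drawing one child per multiple-birth set. In Aim 1 it is handled differently: "We will account for clustering due to twins/triplets in our sample by adding a random effect at the family level".
- Power is stated as above 80% for SNP heritability as low as 21%.

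**The concern.** The defence of I concerns likeness between persons. In the y_it model there is a second kind of likeness, between a child's own two scores, and unrelatedness says nothing about it. Drawing one child per set removes siblings but leaves both of the child's rows in.

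Under V as written, a child's two residuals are independent, so only g can link the two scores. Home, neonatal injury, caregiver and schooling all make a child's scores alike without being genetic, and the model has nowhere else to put them. A reported genetic variance could then arise with no genetic effect at all, at or above the 21% that the plan names as its detectable value.

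**Working it through.** **The plan's own figure.** The above-80% power at 21% cannot be reproduced, because its N, alpha, sidedness and the spread of A are not stated. For a one-score model, SE(h²) ≈ √(2Me)/N, where Me is 1 over the variance of A's off-diagonals. With N = 300 and Me = 250, SE = √500/300 = 0.075, and two-sided 5% power is Φ(0.21/0.0745 − 1.96) = Φ(0.86) = 80%. At N = 300 the claim needs Me of at most about 253 (two-sided) or 321 (one-sided). For Me of 10,000 to 50,000 and N of 256 to 377, power is about 4-14%. So the figure is attainable only with a narrow marker set.

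**Algebra.** Stack the two scores, let Aᵢᵢ ≈ 1, and let c be the share of variance that is stable and non-genetic.
- Model: Cov(yᵢ₀, yᵢ₁) = Aᵢᵢσg² ≈ σg².
- Truth: Cov(yᵢ₀, yᵢ₁) = σg² + σc².
- Between children, the model says Cov = Aᵢⱼσg². This is the only information that separates genes from other stable causes.

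If the Aᵢⱼ are tiny, as with genome-wide SNPs, the within-child covariance dominates and σg² estimates σg² + σc². If they are more spread, as with a few hundred markers, the between-child pairs pull the estimate down, but not to the truth.

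**Simulation inputs.**
- Children: 300 expected to attend (section 17.1). The 55 sets scale to 55 × 300/377 = 43.8; if all are twins, 300 − 43.8 ≈ 256 unrelated children.
- True SNP heritability 0; c assumed, since the documents give no value.
- A from 20,000 independent markers (off-diagonal SD 0.007) or 250 (SD 0.063).
- Reduced model with g but no interactions with g; maximum likelihood; likelihood-ratio test of σg² = 0 with critical value 2.706 (nominal 5%); 120 runs per setting, so the Monte Carlo SE is about 4 points near 60% and 2 points near 5%.

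| c | 20,000 markers: mean estimate, false rejection | 250 markers: mean estimate, false rejection |
|---|---|---|
| 0 | 0.02, 6% | 0.02, 4% |
| 0.2 | 0.20, 96% | 0.08, 60% |
| 0.4 | 0.40, 100% | 0.19, 94% |
| 0.6 | 0.60, 100% | 0.36, 100% |

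The 250-marker estimates are 42%, 48% and 59% of c (from 0.084, 0.190 and 0.355 before rounding). Repeat runs with other seeds and marker counts gave 95-96% and 54-61% at c = 0.2. At c = 0.1 they gave 40-49% with 20,000 or more markers and 22-23% with 200 or 250.

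**Hand check.** With A ≈ I, the test is in effect a one-sided 5% test of the within-child correlation r. By Fisher's z, power = Φ(atanh(r)√253 − 1.645). For r = 0.1 this is Φ(−0.05) = 48%; for r = 0.2 it is Φ(1.58) = 94%.

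**With a child-level term σc² in both null and alternative.** False rejection falls to 0-3% (20,000 markers) and 2-8% (250 markers). With true heritability 0.21 and c = 0.3, the model as written averages 0.51 or 0.39. With the term it averages 0.24 (SD 0.22) or 0.21 (SD 0.07).

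**The interaction test.** With A ≈ I, no genetic effect and equal covariance in both arms, Time×Trt×g rejects 1-3% for c of 0, 0.4 and 0.6. If follow-up SD differs between arms for a non-genetic reason, it rejects 13-17% at a ratio of 1.1 and 54-55% at 1.2 (c of 0 and 0.4 only; 150 runs each).

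**The case against.** Four things can be said for the plan.

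1. *The sentence about I is correct where it stands.* This holds. It belongs to the one-score model, and a heritability estimated from one score per child is unaffected. The fault lies only in carrying V over.
2. *The trial model is described as similar to Aim 1, and Aim 1 has a family random effect.* With one child per family, that effect would act as a child intercept and remove most of the problem. But it is stated for Aim 1, is absent from the V that Aim 2 retains, and is replaced there by resampling. The mention of a structural equation implementation does not supply the missing term either. If the authors mean to keep a family or child effect, the text must say so.
3. *The notation is abbreviated.* Aim 1 also shows only ε_it, yet claims equivalence to ANCOVA, which needs within-child covariance. For Aim 1 that covariance is simply left open. For Aim 2, V is written out and expressly kept.
4. *The size is unknown.* Section 17.1 says that robust measures comparable at all time points are lacking, so the within-child correlation may be modest. This stands as a limit on the size. Yet a share of 0.1 already gives 40-49% false rejection with a genome-wide A.

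A reader might infer that the treatment-by-gene test is invalid too and that Aim 2 cannot answer the secondary objective. The calculations do not support that: Time×Trt×g stays at 1-3% under stable likeness alone. A reader might also take σg² to equal the within-child correlation whatever the markers. That holds for a genome-wide A only, and the documents differ on the marker set: section 2.1 speaks of fatty-acid synthesis genes, section 17.1 of genome-wide SNPs.

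**Conclusion.** Wrong as written, and limited to the genetic variance (heritability) in the two-time-point model. Given V as stated, the direction of the bias follows from the algebra. Its size rests on assumptions: 256 unrelated children, a stable non-genetic share that the documents do not give, and the marker set. At a share of 0.2, false rejection of zero heritability is about 95% with a genome-wide A and about 60% with 250 markers, against a nominal 5%. The interaction test has a separate, conditional weakness: it can be inflated if the arms differ in follow-up spread for non-genetic reasons.

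This should be fixed, but it does not threaten the trial's main result. Aim 2 is secondary, and neither the Aim 1 analysis nor the two-SNP tests use this V.

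**What to change.** In section 17.1, first part of Aim 2:

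1. For the two-time-point model, replace V with Aσg² (expanded over times) + a non-genetic child-level variance σc² + a residual variance allowed to differ by time. Test σg² against a null that keeps σc².
2. Limit the sentence defending I to the one-score model.
3. If a stand-alone heritability is wanted, analyse the age 8½-10½ score alone, one row per child, with V as written. Adding the earlier score as a covariate is not equivalent: it estimates a conditional quantity and drops children missing either score. For example, with unit variances, the same genetic effect at both ages, h² = 0.21 and c = 0.3, the correlation is 0.51 and the conditional value is 0.21 × 0.49²/(1 − 0.51²) ≈ 0.07.
4. Say which markers build A, and limit the above-80% power statement to the model, N, alpha and marker set from which it was derived.

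The cost is wording and one or two variance parameters; no new data. The price is precision. With a genome-wide A and about 256 children, σg² is nearly inseparable from σc²: at a true value of 0.21 the corrected test rejected in 0% (c = 0) and 3% (c = 0.3) of runs. With 250 markers it rejected in 94% and 93%.

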1.0 Study Summary

Study Title	Long-term Effects and Safety of DHA Supplementation in Toddlerhood for Children born Preterm
Study Design	The present follow up study involves a prospective cohort of toddlers born preterm from our previous randomized, double-blind, placebo-controlled Omega Tots trial (ClinicalTrials.gov Identifier: NCT01576783, IRB11-00343, IRB14-00342).
Primary Objective	The primary objective for this study is to determine the long-term effect of daily dietary supplementation at age 1 year with omega-3 docosahexaenoic acid (DHA) and omega-6 arachidonic acid for children born preterm by comparing general cognitive ability, language, and multiple facets of executive function between the intervention and placebo arms at ages 8½ - 10 ½ years.
Secondary Objective(s)	The secondary objective of this study is to determine the role of variability in fatty acid metabolism genetics en masse on the effect of supplementation on short and long-term outcomes, and further focus on 2 previously published FADS2 genetic variants.
Research Intervention(s)/ Investigational Agent(s)	Children from the original Omega Tots trial (NCT01576783) were previously randomized to 180 days of DHA+AA (200mg DHA+200mg AA daily) or placebo (400mg corn oil), dissolving powders in blinded foil packets. At this time, participants will not receive any further intervention or investigational agents. Long-term outcomes will be observed and recorded accordingly across intervention groups
IND/IDE #	112885
Study Population	Participants will be the 377 parent-child dyads from the original Omega Tots trial. They were born at <35 weeks' gestation, were 10-16 months of age (age corrected for prematurity) at trial enrollment, and had been patients at Nationwide Children's Hospital NICU or Follow-up clinic.
Sample Size	All 377 randomized children from the original Omega Tots trial (NCT01576783) will be eligible for in-person follow-up at age 8½ - 10 ½ years.
Study Duration for individual participants	Participants will partake in one comprehensive study visit when children are sometime between 8 years, 180 days and 10 years, 180days of age. It is expected that participant enrollment will begin by September 1, 2020, and that human subjects' activity will be completed by February 1, 2025.

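### Hypothesis 2a names a fatty-acid gene set, but the Aim 2 model builds its relationship matrix from genome-wide SNPs, and the 21% heritability power figure does not cover the treatment-by-gene test

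*Combined protocol and SAP*

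**What the plan says.** Section 1.0 gives the secondary objective as to "determine the role of variability in fatty acid metabolism genetics en masse on the effect of supplementation on short and long-term outcomes". Section 2.1 states hypothesis 2a: "common genetic variant-based heritability over long-chain fatty acid metabolism will be associated with poorer performance on our outcome assessments", in children assigned to DHA+AA compared with placebo. It then fixes the genetic content: "Genetic variation is based on measured SNPs in genes accounting for virtually all synthesis of very long-chain fatty acids".

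Section 17.1 is the only analysis text for 2a. It first sets out a general one-component model, y = β0 + Xβ + g + ε, with V = Aσg² + Iσe². Of the matrix A it says that "in this case the distance is genetic similarity calculated from the genome-wide SNP data". It gives more than 80% "power to detect SNP-based heritabilities as low as 21%, after accounting for the resampling procedure". It supports this by noting that "the relationship between genetics and many metabolism biomarkers in blood is much higher than a heritability of 21" per cent, "giving further reassurance that the study is adequately powered". Only after that does it write the trial model, which contains Trt × g and Time × Trt × g, "while the constraints on V are still imposed". No power, effect size or sample size is attached to that model.

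**The concern.** There are two linked problems.

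First, the gene set in the hypothesis does not reach the model. If an analyst follows section 17.1 literally, g is a genome-wide effect. A treatment interaction with it says nothing specific about fatty-acid synthesis. Two analysts could reasonably build different matrices for the same secondary objective.

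Second, the only power figure belongs to a different quantity. A SNP heritability is the share of outcome variance due to g, with no treatment term in it. Hypothesis 2a is a contrast between arms on developmental outcomes, and blood-biomarker heritability bears on neither the contrast nor those outcomes. A reader of a null treatment-by-gene result could not tell what it rules out.

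**Working it through.** **Inputs from the documents (section 17.1).** Heritability 0.21; power above 80%; 377 randomized; 300 expected to attend; 55 sets of twins or triplets, with one child drawn per set in each resample. Alpha 0.05 is stated for Aim 1 only.

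**Not in the documents.** For this figure: N, alpha, sidedness and the number of SNPs in A. The values below are therefore assumptions.

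**Step 1: unrelated children.** One child per set gives at most 377 − 55 = 322. At 300 attending, with equal attendance, 300 × 322/377 = 256. The ceiling, if resampling recovered all the information, is 377.

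**Step 2: can the plan's own figure be reproduced?** Not without the missing inputs. One can ask when it would hold. Let Me be the effective number of independent SNPs behind A. In large samples SE(h²) = √(2·Me)/N, and one-sided 5% power = Φ(0.21/SE − 1.645). Power of 80% needs SE = 0.21/(1.645 + 0.842) = 0.0845, so Me ≤ (0.0845·N)²/2:

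- N = 256: Me up to about 234
- N = 322: Me up to about 370
- N = 377: Me up to about 507

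A two-sided 5% test lowers these to 184, 291 and 399.

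The formula was checked by simulating the likelihood-ratio test (independent SNPs, one-sided 5%, 1,000 replicates). Power at N = 256 / 322 was:

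- 100 SNPs: 95% / 98%
- 200 SNPs: 81% / 91%
- 300 SNPs: 64% / 84%
- 400 SNPs: 58% / 77%

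Separate runs at N = 256 and 200 SNPs gave 77% to 81%, so the limit there is about 200. The stated power is therefore attainable with a small gene-set matrix.

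**Step 3: the same figure with a genome-wide A.** Me is assumed. One-sided 5% power at heritability 0.21:

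| Me | N = 256 | N = 322 | N = 377 |
|---|---|---|---|
| 5,000 | 13.4% | 16.6% | 19.7% |
| 10,000 | 10.3% | 12.2% | 13.9% |
| 50,000 | 7.0% | 7.6% | 8.2% |

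Example: Me = 5,000 and N = 256 give SE = 100/256 = 0.391, and Φ(0.21/0.391 − 1.645) = 13.4%. Simulation (300 replicates) gave 12% in that cell, and about 4% at 50,000 SNPs for N = 256 and 322. At the high end the formula is, if anything, generous.

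**Step 4: does the 21% figure carry over to the interaction?** Suppose it is exactly true: 80% power at 0.21, so SE = 0.0845. These are illustrations with one time point and equal arms, not power for the planned model.

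- Treatment coded ±1 and the interaction carrying its own variance of 0.21: the SE is about unchanged, so power is about 80%.
- A difference between arm-specific heritabilities: each arm has N/2, so its SE doubles, and the difference adds √2. The SE is 0.0845 × 2.83 = 0.239. The detectable difference becomes 0.21 × 2.83 = 0.59. Power for a 0.21 difference is Φ(0.21/0.239 − 1.645) = 22%.

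The same 21% statement is thus compatible with about 22% or about 80% power, depending on choices that the plan does not state.

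**The case against.** The best defence is to read sections 2.1 and 17.1 together: the hypothesis supplies the SNP set and the analysis section supplies the machinery. The genome-wide wording sits in a general description of the method, and the power figure is attainable only with a small matrix, which suggests that a gene-set A was intended. That is a fair inference and makes the repair short. It does not remove the need for it: the trial model keeps the same variance constraints, and no other definition of A is given. Elsewhere in section 17.1, for the separate exploratory gene-expression analysis, the plan does write out a fatty-acid gene limit.

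Three stronger readings are tempting, and the documents do not support them.

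- A reader might infer that the 21% figure is an arithmetic error. None is shown, because the inputs needed to recompute it are absent.
- A reader might infer that the plan expressly claims adequate power for the interaction. It says this of the study, before the trial model appears. The Aim 2 heading invites the inference but does not state it.
- A reader might infer that 2a is underpowered. Interaction power depends on treatment coding, SNP number and interaction variance, none of which is stated.

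**Conclusion.** The concern holds as a mismatch between hypothesis and model, together with a power figure that does not cover the planned test. As written, A does not carry the gene set that defines 2a. With a genome-wide A, power at 21% heritability would be about 7% to 20%, assuming 5,000 to 50,000 effective SNPs, N of 256 to 377 and a one-sided 5% test. With a gene-set A, 80% is within reach up to roughly 200 to 500 effective SNPs over the same N. The figure itself can be neither confirmed nor refuted.

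That the figure concerns a main genetic variance does not depend on any assumed SNP number. It follows from the definition of heritability and from where the figure stands in the text. The missing interaction power is not peculiar to 2a: the FADS2 single-SNP tests of 2b do not use A or the 21% figure, but section 17.1 gives no power for their Time × Trt × SNP term either. The primary comparison in Aim 1 is untouched.

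**What to change.** In section 17.1, under Aim 2:

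- Define A for the 2a test from the fatty-acid gene-set SNPs named in section 2.1, keep genome-wide SNPs for the ancestry components, and state how many SNPs enter A.
- Restate the 21% figure as power for a main genetic variance, with its unrelated N, alpha and sidedness.
- Do not rest the claim of adequate power on that figure for the treatment-by-gene test. Either give a detectable treatment-by-gene effect on the study outcomes, with the treatment coding and interaction variance assumed, or say that none was calculated and label 2a exploratory.
- For 2b, say that no interaction power was calculated.

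This needs no new data. The cost is some extra calculation, for which the unstated inputs must first be fixed, and possibly a less favourable power statement for a secondary objective.
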